12.0 STUDY COMMITTEES AND COMMUNICATIONS

Each of planned study committees will have a charter outlining its activities and responsibilities. In brief, the purpose of each committee is as follows:

- **Independent EAC:** Adjudication of hemostatic efficacy, deaths, TEs, and post-surgical bleeding events for all patients. The EAC will be blinded to all anti-fXa levels.
- **Independent DSMB:** Monitor all safety data and make recommendations for study modification or stopping due to safety reasons.

13.0 INVESTIGATOR AND ADMINISTRATIVE REQUIREMENTS

13.1. Institutional Review Board or Independent Ethics Committee

The protocol and ICF for this study must be reviewed and approved by an appropriate IRB or IEC before patients are enrolled in the study. It is the responsibility of the Investigator to assure that the study is conducted in accordance with current country and Local Regulations, ICH, GCP, and the Declaration of Helsinki. A letter, documenting the approval that specifically identifies the protocol by number and title as well as the Investigator, must be received by the Sponsor Pharmaceuticals, Inc. before initiation of the study. Amendments to the protocol will be subject to the same requirements as the original protocol.

After the completion or termination of the study, the Investigator will submit a report to the IRB or IEC, and to the Sponsor.

13.2. Informed Consent

Each patient must be provided with oral and written information describing the nature and duration of the study, and the patient must sign a written ICF in a language in which he/she is fluent before study-specific procedures are conducted. The signed and dated ICF will be retained with the study records. Each patient will also be given a copy of his/her signed ICF. Due to the critical nature of the illness under study and the possibility that patients will be unable to provide their own consent, proxy consents (defined as consent from a legally authorized representative) are allowed if permissible by national regulatory authorities or local/regional laws and regulations. Emergency consent is not permitted.

13.3. Documentation

The Investigator must provide the Sponsor with the following documents (copies of which must be maintained by the Investigator):

1. Curriculum vitae of the Investigator and any sub-investigators listed on the Form FDA 1572.
2. A signed copy of the IRB or IEC approval notice for protocol and informed consent.
3. A copy of the IRB- or IEC-approved ICF.
4. Laboratory certification with a list of normal values for laboratory tests that will be conducted at local laboratories.
5. Completed financial disclosure form for the Investigator and any sub-investigators listed on the Form FDA 1572.

13.4. Data Collection and Management Responsibilities

Data collection is the responsibility of the clinical trial staff at the site under the supervision of the site Investigator. The Investigator is responsible for ensuring the accuracy, completeness, legibility, and timeliness of the data reported.

All source documents should be completed in a neat, legible manner to ensure accurate interpretation of data. Data recorded in the eCRF derived from source documents should be consistent with the data recorded on the source documents.

Clinical data (including AEs, concomitant medications, and expected adverse reactions data) and clinical laboratory data will be entered into a 21 Code of Federal Regulations (CFR) Part 11-compliant EDC system, as appropriate. The data system includes password protection and internal quality checks, such as automatic range checks, to identify data that appear inconsistent, incomplete, or inaccurate. Clinical data will be entered directly from the source documents. Some clinical laboratory data will be collected externally from the EDC systems. Further details for data collection and data handling will be specified in the data management plan, eCRFs, instructions for completing forms, other data handling procedures, and procedures for data monitoring. The MedDRA coding dictionary will be used for coding AEs, medical history conditions, and procedures. The reconciliation of the SAEs between the clinical and safety databases will be conducted as specified in plans determined and approved prior to study start-up. The WHO-DD dictionary will be used to code medications.

13.5. Study Records Retention

Study documents should be retained for a minimum of 2 years after the last approval of a marketing application in an ICH region and until there are no pending or contemplated marketing applications in an ICH region or until at least 2 years have elapsed since the formal discontinuation of clinical development of the study intervention. These documents should be retained for a longer period, however, if required by local regulations. No records will be destroyed without the written consent of the Sponsor, if applicable. It is the responsibility of the Sponsor to inform the Investigator when these documents no longer need to be retained.

13.6. Deviation from the Protocol

The Investigator will not deviate from the protocol. In medical emergencies, the Investigator will use medical judgment and will remove the patient from immediate hazard, and then notify the Sponsor's Medical Monitor and the IRB or IEC immediately regarding the type of emergency and course of action taken. Any action in this regard will be recorded on the appropriate eCRF. Deviations due to non-compliance that render subject non-evaluable for key endpoints will be considered significant deviations. Any other changes in the protocol will be made as an amendment to the protocol and must be approved by the Sponsor and the IRB or IEC — before the changes or deviations are implemented. The Sponsor will not assume any

responsibility or liability for any deviation or change that is not described as part of an amendment to the protocol.

13.7. Disclosure of Data

Individual patient medical information obtained as a result of this study is considered confidential and disclosure to third parties other than those noted below is prohibited. Patient confidentiality will be further assured by utilizing patient identification code numbers to correspond to treatment data in the computer files. The study personnel, employees of the regulatory agencies, including the US FDA and the study sponsor and its agents will need to review patient medical records in order to accurately record information for this study. If results of this study are reported in medical journals or at meetings, the patient's identity will remain confidential. Conduct of this study will comply with the EU's General Data Protection Regulation.

13.8. Drug Accountability

The Investigator must maintain accurate records of the amounts and dates andexanet was received from the Sponsor and prepared for the study, including the volume and concentration of stock solution prepared and remaining stock solution volume after dose preparation. All drug supplies must be accounted for at the termination of the study and a written explanation provided for any discrepancies. All partially used or unused drug supplies can be destroyed at the site if available, in accordance with approved written procedures, or returned to the Sponsor after written authorization is obtained from the Sponsor's Clinical Development. In addition, no onsite destruction or drug returns will be performed without having accountability and verification of study drug performed first. The Investigator will maintain a record of the amount and dates when unused supplies were either destroyed or returned to the Sponsor. All records will be retained as noted in Section 13.5.

13.9. Study Monitoring

The Investigator will allow representatives of the Sponsor to periodically review (at mutually convenient times before, during, and after the study has been completed) all eCRFs and relevant portions of office, clinical, and laboratory records for each patient. Appropriate source documents, including documents that support patients' eligibility (e.g., medical history, concomitant medications) should be made available to the study monitor. The monitoring visits provide the Sponsor with the opportunity to evaluate the progress of the study; verify the accuracy and completeness of eCRFs; assure that all protocol requirements, applicable regulations, and Investigator's obligations are being fulfilled; and resolve any inconsistencies in the study records.

15.0 LIST OF APPENDICES

Appendix A: Schedule of Activities

Appendix B: Disseminated Intravascular Coagulation (DIC) Scoring Algorithm [33]

Appendix C: Definitions of Cardiogenic Shock, Sepsis and Septic Shock [34]

Appendix D: Definition of Female of Childbearing Potential

Appendix E: Guidance for Submission of Potential Thrombotic Events for Adjudication

Appendix F: American Society of Anesthesiologists Physical Status Classification

APPENDIX A. SCHEDULE OF ACTIVITIES

STUDY DAY:	Screening & Baseline		Treatment					Follow-Up		
			1			2		3		30 or ET
TIME POINT AND WINDOW:			SURGERY		Post-Surgery					
	-2 hours to -45 min relative to SoS	-45 min to -30 min relative to SoS	-30 min to -5 min relative to SoS	End of Bolus ± 15 min	EoII -15 min	EoS [1] + 15 min [2]	EoS + 6 h ± 1 h	EoS + 12 h ± 1 h	EoS + 24 h ± 1 h	EoS + 48 h ± 1 h
Obtain Consent	X									
Determine Eligibility	X									
Obtain Medical History	X									
Demographics	X									
Obtain Prior Medications and Time of Last Anticoagulant Dose or Plasma Level	X									
Obtain ASA Class			X							
Vital Signs (BP, HR, RR, temp)	X	X		X	X	X	X	X	X	X
Weight (actual reported/recent)	X									X
Physical Examination	X							X	X	X
Central Labs: Anti-fXa and anti-IIa Activity		X (pre- ADX)		X	X	X	X			
Central Labs: Thrombin Generation		X (pre- ADX)		X	X	X	X	X	X	
Central Labs: Antibodies to andexanet, HCPs, and FX/FXa (modified Bethesda); and nAb (andexanet)	X (pre- ADX)									X

		Screening & Baseline	Treatment					Follow-Up					
STUDY DAY:		1							2	3	30 or ET		
TIME POINT AND WINDOW:			SURGERY			Post-Surgery		EoS [1] + 15 min [2]	EoS + 6 h ± 1 h	EoS + 12 h ± 1 h	EoS + 24 h ± 1 h	EoS + 48 h ± 1 h	+ 7 days
	-2 hours to -45 min relative to SoS	-45 min to -30 min relative to SoS	-30 min to -5 min relative to SoS	End of Bolus ± 15 min	EoII -15 min								
Central Labs: TFPI activity		X (pre-ADX)		X	X	X		X	X	X	X	X	
Local Labs: PT-INR	X												
Local Labs: Chemistry and Pregnancy Test [3]	X												
Local Labs: CBC		X				X		X				X	
Prepare Andexanet	X												
Administer Andexanet Bolus, Immediately Followed by an Infusion			X										
Assess Need for Extended Andexanet Infusion (if surgery ongoing)					X [4]								
Estimate Predicted Blood Loss			X [5]										
Surgical Intervention				SURGERY									
Record Blood Loss Post Surgery						X							
Record Investigator Assessment of Intraoperative Hemostasis						X							
Record Blood Products & Hemostatic Treatments [6]			X										

STUDY DAY:	Screening & Baseline		Treatment						Follow-Up		
			1						2	3	30 or ET
TIME POINT AND WINDOW:			SURGERY			Post-Surgery			EoS + 24 h ± 1 h	EoS + 48 h ± 1 h	+ 7 days
	-2 hours to -45 min relative to SoS	-45 min to -30 min relative to SoS	-30 min to -5 min relative to SoS	End of Bolus ± 15 min	EoII -15 min	EoS [1] + 15 min [2]	EoS + 6 h ± 1 h	EoS + 12 h ± 1 h			
Record Bleeding-Related Diagnostic & Therapeutic Procedures [7]			X						X	X	
Record Volume of Colloid and Crystalloid [6]			X								
Record Hours in ED, PACU, ICU/Critical Care, General Hospital Floor, and Total as an Inpatient											X
Record AEs and any TEs	X		X						X	X	X
Record Concomitant Medications	X		X						X	X	X
Ascertain Survival Status											X

ADX = andexanet; AE = Adverse event; ASA = American Society of Anesthesiologists; BP = Blood pressure; CBC = Complete blood count; ED = Emergency department; EoII = End of Initial Infusion; EoS = End of Surgery; ET = Early Termination; FX = Factor X; FXa = Activated factor X; h = Hour(s); HCP = Host-cell protein; HR = Heart rate; ICU = Intensive care unit; INR = International normalized ratio; min = Minute(s); nAb = Neutralizing antibody (activity); OR = operating room; PACU = Post-anesthesia care unit; PT = Prothrombin time; RR = Respiratory rate; SoS = Start of Surgery; TE = thrombotic event; Temp = Temperature; TFPI = Tissue factor pathway inhibitor

¹ The EoS time point may occur before the EoII; EoS procedures should be carried out when EoS occurs.

² Collect EoS samples within 15 minutes from the end of surgery but before stopping infusion.

³ Pregnancy test in women of childbearing potential; test may be done on urine or serum.

⁴ Approximately 30-45 minutes prior to the end of the andexanet infusion, the investigator should inform the pharmacy whether additional andexanet will be needed, to allow time for preparation.

⁵ Prior to the first incision, predicted blood loss must be determined by the investigator.

⁶ Colloid, crystalloid, hemostatic agents, and blood products administered prior to arrival in the ED should also be recorded.

⁷ Record procedures performed to evaluate bleeding source/extent and for treatment of bleeding.

		Re-Dose of Andexanet		
STUDY DAY:		1		
TIME POINT AND WINDOW:		Pre-Start of Bolus -15 min	End of Bolus +15 min	Pre-End of Infusion -15 min
Initiate Andexanet Low Dose Bolus + Infusion		X		
Central Labs: Anti-fXa and anti-IIa Activity		X (pre-ADX)	X	X

APPENDIX B. DISSEMINATED INTRAVASCULAR COAGULATION (DIC) SCORING ALGORITHM [33]

Note: Algorithm should only be used for patients with an underlying disorder known to be associated with overt DIC. A score of ≥ 5 is compatible with overt DIC.

Laboratory Test	Result	Score
Platelet Count	$\geq 100 \times 10^9 / L$	0
	$< 100 \times 10^9 / L$	1
	$< 50 \times 10^9 / L$	2
D-Dimer, Fibrin Degradation Products	No increase	0
	Moderate increase	2
	Strong increase	3
Prothrombin Time	< 3 seconds	0
	≥ 3 but < 6 seconds	1
	≥ 6 seconds	2
Fibrinogen Level	≥ 1 g/L	0
	< 1 g/L	1

APPENDIX C. DEFINITIONS OF CARDIOGENIC SHOCK, SEPSIS AND SEPTIC SHOCK [34]

Cardiogenic shock is a cardiac disorder that results in both clinical and biochemical evidence of tissue hypoperfusion [35]. The definition of cardiogenic shock may be clinically determined and consists of the following: Systolic blood pressure (SBP) < 90 mmHg for at least 30 minutes, OR

- Hemodynamic support required to maintain SBP ≥ 90 mmHg, AND
- End-organ hypoperfusion (e.g., urine output < 30 mL/hr or cool extremities)

Cardiogenic shock may also be optionally defined by hemodynamic criteria obtained through invasive hemodynamic monitoring:

- Cardiac index ≤ 2.2 L/min/m², AND
- Pulmonary capillary wedge pressure ≥ 15 mmHg

Sepsis is defined as life-threatening organ dysfunction caused by a dysregulated host response to infection [36]. Organ dysfunction can be identified as an acute change in total Sequential [sepsis-related] Organ Failure Assessment (SOFA) score ≥ 2 points consequent to the infection (Table 4) [37].

- The baseline SOFA score can be assumed to be zero in patients not known to have preexisting organ dysfunction.
- A SOFA score ≥ 2 reflects an overall mortality risk of approximately 10% in a general hospital population with suspected infection. Even patients presenting with modest dysfunction can deteriorate further, emphasizing the seriousness of this condition and the need for prompt and appropriate intervention, if not already being instituted.
- In lay terms, sepsis is a life-threatening condition that arises when the body's response to an infection injures its own tissues and organs.
- Patients with suspected infection who are likely to have a prolonged ICU stay or to die in the hospital can be promptly identified at the bedside with the Quick SOFA (qSOFA) criteria, i.e., alteration in mental status, systolic blood pressure ≤ 100 mmHg, or respiratory rate ≥ 22 /min [36].

Septic shock is a subset of sepsis in which underlying circulatory and cellular/metabolic abnormalities are profound enough to substantially increase mortality.

- Patients with septic shock can be identified with a clinical construct of sepsis with persisting hypotension requiring vasopressors to maintain mean arterial pressure ≥ 65 mmHg and having a serum lactate level > 2 mmol/L (18 mg/dL) despite adequate volume resuscitation. With these criteria, hospital mortality is in excess of 40%.

Table A4: SOFA Scoring System

Component	Score
PaO₂/FiO₂ (mmHg)	
≥ 400	0
≥ 300 and < 400	+1
≥ 200 and < 300	+2
≥ 100 and < 200 AND mechanically ventilated	+3
< 100 AND mechanically ventilated	+4
Glasgow Coma Scale	
15	0
13-14	+1
10-12	+2
6-9	+3
< 6	+4
Hemodynamic Criteria	
Mean arterial pressure ≥ 70 mmHg	0
Mean arterial pressure < 70 mmHg	+1
Dopamine dose ≤ 5 µg/kg/min OR dobutamine (any dose)	+2
Dopamine > 5 µg/kg/min OR epinephrine ≤ 0.1 µg/kg/min OR norepinephrine ≤ 0.1 µg/kg/min	+3
Dopamine > 15 µg/kg/min OR epinephrine > 0.1 µg/kg/min OR norepinephrine > 0.1 µg/kg/min	+4

APPENDIX D. DEFINITION OF FEMALE OF CHILDBEARING POTENTIAL

All women of childbearing potential (including those who have had a tubal ligation) will have a urine or serum pregnancy test at screening. If the pregnancy test is positive, andexanet should not be administered.

All female patients are considered to be of childbearing potential unless they meet 1 of the following criteria:

1. The patient has been post-menopausal (amenorrheic) for at least 1 year.
2. The patient had a surgical bilateral oophorectomy (with or without hysterectomy) more than 6 weeks prior to screening.
3. The patient had a hysterectomy.

APPENDIX E. GUIDANCE FOR SUBMISSION OF POTENTIAL THROMBOTIC EVENTS FOR ADJUDICATION

Adjudication criteria for the diagnosis transient ischemic attacks, strokes, myocardial infarctions (MIs), venous thromboembolism, and arterial systemic embolism are provided below.

Transient Ischemic Attack (TIA) is defined as a transient episode of neurological dysfunction caused by focal brain, spinal cord, or retinal ischemia, with signs or symptoms lasting < 24 hours and no evidence of new infarct on neuroimaging if performed. Investigators should consider submitting cases for adjudication if an event meets this definition.

Stroke is defined as an acute episode of neurological dysfunction consistent with a vascular cause. A stroke will be considered to have occurred if there is a rapid onset of signs and/or symptoms of a new persistent neurological deficit consistent with an obstruction to cerebral blood flow with no apparent nonischemic cause (e.g., trauma, tumor, or infection). Signs or symptoms must last at least 24 hours or, for symptom onset less than 24 hours, have neuroimaging evidence of new infarct. Available neuroimaging studies will be considered to support the clinical impression and to determine if there is a demonstrable lesion compatible with an acute stroke. For the diagnosis of stroke, the following criteria must be fulfilled:

- Rapid onset of a focal/global neurologic deficit with at least 1 of the following: change in level of consciousness, hemiplegia, hemiparesis, numbness, or sensory loss affecting 1 side of the body, dysphagia/aphasia, hemianopia, amaurosis fugax, or other new neurological signs/symptoms consistent with stroke.
- The duration of a focal/global neurologic deficit is at least 24 hours, OR the neurological deficit results in death, OR there is neuroimaging evidence of a new infarct.
- There is no other readily identifiable non-stroke cause for the clinical presentation (e.g., brain tumor, trauma, infection, hypoglycemia, peripheral lesion).
- Confirmation of the diagnosis by at least 1 of the following: specialist evaluation, or brain imaging procedure (i.e., computed tomography [CT] scan, magnetic resonance imaging [MRI] scan, cerebral vessel angiography).

If the acute neurological signs represent a worsening of a previous (baseline) deficit, the new signs must have either persisted for more than 1 week, or persisted for more than 24 hours and were accompanied by an appropriate new imaging finding.

Investigators should consider submitting cases for adjudication as a possible stroke if they meet 1 or more of the above criteria, or have potential symptoms and/or conditions (e.g., delirium, mental status changes) that are not otherwise explainable by an alternative etiology.

Since the adjudication of hemostatic efficacy encompasses changes in clinical neurologic function and hematoma volume, these findings will only be considered for thrombotic event adjudication if they clearly have an ischemic etiology.

Myocardial Infarction (MI) should be used when there is evidence of myocardial necrosis in a clinical setting consistent with acute myocardial ischemia. Under these conditions any one of the following criteria meets the diagnosis of MI:

- Detection of a risk and/or fall of cardiac biomarker values (preferably cardiac troponin [cTn]) with at least 1 value above the upper limit of normal (ULN) and with at least 1 of the following:
 - Symptoms of ischemia.
 - New or presumed new significant ST-segment-T wave (ST-T) changes or new left bundle branch block.
 - Development of pathological Q waves in the electrocardiogram (ECG).
 - Imaging evidence of new loss of viable myocardium or new regional wall motion abnormality.
 - Identification of an intracoronary thrombus by angiography or autopsy.
- Cardiac death with symptoms suggestive of myocardial ischemia and presumed new ischemic ECG changes or new left bundle branch block (LBBB), but death occurred before biomarkers were obtained, or before cardiac biomarker values would be increased.
- Percutaneous Coronary Intervention (PCI) related MI is arbitrarily defined by elevation of cTn values ($> 5 \times$ ULN) in patients with normal baseline values or a rise of cTn values $> 20\%$ if the baseline values are elevated and are stable or falling. In addition, either (i) symptoms suggestive of myocardial ischemia, (ii) new ischemic ECG changes, (iii) angiographic findings consistent with a procedural complication, or (iv) imaging demonstration of new loss of viable myocardium or new regional wall motion abnormality are required.
- Stent thrombosis associated with MI when detected by coronary angiography or autopsy in the setting of myocardial ischemia and with a rise and/or fall of cardiac biomarker values with at least 1 value above the ULN.
- Coronary artery bypass grafting (CABG) related MI is arbitrarily defined by elevation of cardiac biomarker values ($> 10 \times$ ULN) in patients with normal baseline cTn values. In addition, either (i) new pathological Q waves or new LBBB, (ii) angiographic documented new graft or new native coronary artery occlusion, or (iii) imaging evidence of new loss of viable myocardium or new regional wall motion abnormality.

Investigators should consider submitting cases for adjudication as a possible MI if they meet 1 or more of the above criteria, or have potential symptoms and/or conditions (e.g., angina, ventricular tachyarrhythmia, cardiogenic shock, heart failure) that are not otherwise explainable by an alternative etiology.

Venous Thromboembolism is defined as a symptomatic deep vein thrombosis (DVT) or PE confirmed by objective testing. Criteria for the objective confirmation of DVT include:

- A constant filling defect in 2 or more views on contrast venography in 1 or more proximal venous segments (iliac, common femoral, superficial femoral, popliteal).
- New or previously undocumented non-compressibility of 1 or more venous segments on compression ultrasound.
- A clearly defined intraluminal filling defect on contrast enhanced CT.

Criteria for the objective confirmation of PE include:

- An intraluminal filling defect on pulmonary angiography.
- Sudden contrast cut-off of 1 or more vessels more than 2.5 mm in diameter on a pulmonary angiogram.
- A high probability ventilation-perfusion (VQ) scan (1 or more segmental perfusion defects with corresponding normal ventilation).
- An abnormal non-high VQ scan plus criteria for the diagnosis of DVT.
- An unequivocal, intra-arterial, un-enhancing filling defect in the central pulmonary vasculature (pulmonary trunk, main pulmonary arteries, anterior trunk, right and left interlobar and lobar arteries) on CT.

Investigators should consider submitting cases for adjudication as a possible VTE if they meet 1 or more of the above criteria, or have potential symptoms and/or conditions (e.g., lower extremity swelling, respiratory failure) that are not otherwise explainable by an alternate etiology. All cases of unexplained sudden death should also be submitted for adjudication as a possible PE and/or MI.

Arterial systemic embolism is defined as abrupt vascular insufficiency associated with clinical and other objective evidence of arterial occlusion in the absence of other likely mechanisms. Clinical signs and symptoms must be consistent with embolic arterial occlusion, and there must be clear evidence of abrupt occlusion of a systemic artery, with at least 1 type of supporting evidence, such as surgical report indicating evidence of arterial embolism, pathological specimens related to embolism removal, imaging evidence consistent with arterial embolism, or autopsy report. Investigators should consider submitting potential systemic arterial embolism cases for adjudication if they meet this definition.

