4.2. Exclusion Criteria

If a patient meets any of the following criteria, he or she is *not* eligible to participate:

1. Surgery for which the risk of clinically meaningful uncontrolled or unmanageable bleeding is low.
2. Acute life-threatening bleeding (ISTH criteria [32]) at the time of Screening:
 - a. The patient has acute-overt bleeding that is potentially life-threatening, e.g., with signs or symptoms of hemodynamic compromise, such as severe hypotension, poor skin perfusion, mental confusion, low urine output that cannot be otherwise explained.
 - b. The patient has overt bleeding associated with a fall in hemoglobin level by ≥ 2 g/dL, OR, a hemoglobin ≤ 8 g/dL if no baseline hemoglobin is available.
 - c. The patient has acute bleeding in a critical area or organ, such as pericardial, intracranial, or intraspinal.

3. Any surgical procedure that involves the intraoperative use of systemic, intravascular, unfractionated heparin.
4. Primary procedure being considered for efficacy evaluation is a non-surgical interventional procedure (e.g., skin biopsy, lumbar puncture, cardiac catheterization, endoscopic retrograde cholangio-pancreatography).
5. Expected survival of < 1 month due to comorbidity.
6. Known “Do Not Resuscitate” order or similar advanced directive.
7. The patient has a recent history (within 30 days prior to Screening) of a diagnosed TE as follows: VTE (including DVT, PE, intracardiac thrombus); MI (including asymptomatic troponin elevations); disseminated intravascular coagulation (DIC); acute traumatic coagulopathy; cerebrovascular accident; transient ischemic attack; unstable angina pectoris hospitalization; or severe peripheral vascular disease (see [Appendix B](#) for DIC scoring algorithm).
8. Acute decompensated heart failure or cardiogenic shock at the time of screening (see [Appendix C](#) for cardiogenic shock definition).
9. The patient has sepsis or septic or hemorrhagic shock at the time of Screening (see definition in Appendix C).
10. The patient has heparin-induced thrombocytopenia (with or without thrombosis).
11. Inherited coagulopathy (e.g., anti-phospholipid antibody syndrome, protein C/S deficiency, Factor V Leiden) at time of Screening.
12. Platelet count < 80,000/ μ L at the time of Screening.
13. Last dose of apixaban < 2.5 mg, rivaroxaban < 10 mg, edoxaban < 30 mg, enoxaparin < 40 mg.
14. The patient is pregnant or a lactating female.

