11.5.1. Definitions

Hemostasis will be assessed from the start of surgery to the end of the procedure. Categories for the assessment of intraoperative hemostasis are provided in Table 3.

Table 3: Intraoperative Hemostasis Categories

Category	Definition
Excellent	Normal hemostasis during the procedure
Good	Mildly abnormal hemostasis as judged by quantity or quality of blood loss (e.g., slight oozing from surgical wounds)
Moderate	Moderate abnormality in intraprocedural hemostasis (e.g., controllable bleeding) but no need for additional systemic procoagulant products *
Poor	Severe hemostatic abnormality during the procedure (e.g., severe refractory hemorrhage) and need for additional systemic procoagulant products *

* Tranexamic acid excluded.

The evaluation period for anti-fXa activity covers the period of time from 5 minutes following the end of the andexanet bolus to just prior to the end of the andexanet infusion. The baseline measurement will be the last value obtained prior to andexanet treatment.

The hemostasis evaluation would exclude unexpected blood loss due to surgical complications that may cause uncontrolled bleeding, such as unintended injury of a major vessel or parenchymal tissue.

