11.5.2. Efficacy Endpoints

11.5.2.1. *Primary Efficacy Endpoint*

The primary efficacy endpoint is the achievement of effective hemostasis, as determined by the surgeon's assessment of intraoperative hemostasis and confirmed by adjudication by an independent EAC (see Table 3).

For each patient, hemostasis will be considered to be effective if the intraoperative hemostasis category is Excellent or Good, and ineffective if the intraoperative hemostasis category is Moderate or Poor.

A patient will be deemed non-evaluable if s/he meets the criteria specified in the EAC Charter.

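### Appendix E admits neurologic findings to thrombotic-event adjudication only if clearly ischemic, for a reason the trial's own hemostasis endpoint does not support and by a test stricter than its own stroke definition

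*Protocol*

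**What the plan says.** Appendix E tells investigators which events to send to the EAC as possible TEs. After the stroke criteria it sets a low bar for submission: any one criterion, or symptoms and conditions without another explanation ("e.g., delirium, mental status changes) that are not otherwise explainable by an alternative etiology"). The next paragraph then narrows what counts. It opens with a reason, "Since the adjudication of hemostatic efficacy encompasses changes in clinical neurologic function and hematoma volume", and draws the consequence that "these findings will only be considered for thrombotic event adjudication if they clearly have an ischemic etiology".

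The endpoint that this reason refers to is defined elsewhere. Section 11.5.1 gives the window, "Hemostasis will be assessed from the start of surgery to the end of the procedure", and the scale, "Categories for the assessment of intraoperative hemostasis are provided in Table 3". Section 11.5.2.1 gives the rule: "hemostasis will be considered to be effective if the intraoperative hemostasis category is Excellent or Good". Section 7.3 adds that bleeding after surgery, once confirmed by the EAC, counts as poor hemostatic efficacy.

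The stroke definition in Appendix E asks for a new deficit "consistent with an obstruction to cerebral blood flow with no apparent nonischemic cause". Section 8.2 makes every submitted event a suspected TE and tracks both suspected and confirmed TEs as safety endpoints.

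**The concern.** The restriction rests on a stated premise, and the premise does not match this trial's endpoint. If neurologic change belonged to the efficacy endpoint, as it might in a trial of intracranial hemorrhage, it would make sense to keep it out of the thrombotic count unless it was plainly ischemic. Here there is no index bleed whose neurologic course is being scored, so the sentence reaches any new neurologic change after surgery.

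TEs are the adverse event of special interest (Section 9.1.3) and a key safety parameter (Section 3.7). The trial has one arm (Section 11.2), so the absolute TE rate is itself the safety result, and no control group shares any loss of events. The study is also meant to inform a randomized Phase 3 trial (Section 3.1). A rule that can only remove events from this count needs a sound reason.

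**Working it through.** The check is mainly textual. No sample size, power or alpha figure depends on it.

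**1. The premise against the endpoint.** The four categories of Table 3 turn on how abnormal hemostasis was during the procedure and whether systemic procoagulant products were needed. None mentions neurologic function or hematoma volume, and the window closes at the end of surgery. Section 7.3 brings in postoperative bleeding as a yes/no finding, with no neurologic or volume measure. Patients bleeding into a critical site at screening are excluded under Section 4.2: "The patient has acute bleeding in a critical area or organ, such as pericardial, intracranial, or intraspinal". Within the protocol, nothing supports the premise.

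**2. The two thresholds.**

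| Place in Appendix E | Test |
|---|---|
| Stroke definition | Consistent with obstructed flow; no nonischemic cause apparent |
| Submission rule | Any one criterion, or unexplained symptoms such as delirium |
| Disputed sentence | Ischemic cause must be clear |

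The first test is passed when no competing cause is seen. The third needs positive evidence of ischemia, so it is the stricter.

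**3. A case that separates them.** Take a rapid-onset deficit two days after surgery that lasts more than 24 hours, is confirmed by a specialist, fits obstructed flow, and has no other cause in sight but no infarct on imaging. The stroke criteria accept duration in place of imaging evidence, and specialist evaluation in place of an imaging procedure. The case meets the definition, yet a committee could fairly say that its ischemic cause is not clear and set it aside. The MI and VTE guidance in the same appendix has no such extra test.

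**4. Which counts are exposed.** The confirmed count is exposed directly, because the sentence limits what is considered in adjudication. The suspected count depends on submission (Section 8.2), so it is exposed only if sites read the sentence as a reason not to submit. That reading is possible, since the appendix is addressed to investigators and Section 8.2 sends them there to decide.

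**5. Size: an illustration only.** The protocol's figure for ANNEXA-4 (Section 1.4.7) reproduces: 34/352 = 0.0966, or 9.7%. Assume 100 treated patients and 10 true confirmed TEs, and let k be the number set aside. With x = 10 − k, the exact 95% limits are the 0.025 quantile of Beta(x, 101 − x) and the 0.975 quantile of Beta(x + 1, 100 − x).

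| k (assumed) | Confirmed TE rate | Exact 95% CI |
|---|---|---|
| 0 | 10% | 4.9 to 17.6% |
| 1 | 9% | 4.2 to 16.4% |
| 2 | 8% | 3.5 to 15.2% |
| 3 | 7% | 2.9 to 13.9% |

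No row is a forecast. For scale, the treatment-related SAEs listed for ANNEXA-4 include ischemic stroke in 3 patients, and cerebral infarction and cerebrovascular accident in 2 each. That is 7/352 = 2.0%, or about 2 per 100 if no patient is counted twice. Strokes of any cause could be more frequent. Against that figure, k = 2 would remove about all such events, including plainly ischemic ones that pass either test. ANNEXA-4 was also 64% intracranial hemorrhage, which is excluded here when acute at screening.

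**The case against.** The strongest reply is that the sentence has a purpose. Spinal cord decompression is an eligible example (Section 3.4.1) and neurosurgery is a planned subgroup (Section 11.9). Excluding critical-site bleeding at screening does not prevent it after surgery. A postoperative hematoma with neurologic decline could count as poor hemostatic efficacy through Section 7.3, and it should not also be counted as a thrombotic event. The EAC charter, which is not shown, may set this out. This stands in part: the mismatch is established against the protocol text only. However, a deficit caused by a hematoma already fails the stroke definition, because it has an apparent nonischemic cause. The added test is not needed for that purpose.

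A second reply is that the sentence governs adjudication, not submission, so it does not formally contradict the submission rule before it. That is a fair reading, and it is why the suspected count is only conditionally exposed.

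A reader might go further and infer that strokes will be under-counted, or that both TE counts are biased down. The documents do not show this. TIA and stroke are ischemic by definition here, and a typical ischemic stroke passes either test. Nor is it right that nothing else would catch the events. All treatment-emergent adverse events are reported until 30 days after the last dose whatever their cause (Section 9.2.1), the EAC adjudicates deaths and post-surgical bleeding, and the Data Safety Monitoring Board sees all safety data (Section 3.5). What may be lost is classification as a TE.

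**Conclusion.** The point holds as an internal inconsistency in the guidance for a key safety endpoint. The reason given for the restriction is absent from the protocol's endpoint definition, and its test is stricter than the stroke definition beside it. Events of undetermined mechanism that meet that definition may be left out of the confirmed TE count, and out of the suspected count if sites take the sentence as a submission filter.

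The direction of any bias is certain: the rule can only lower the count. Its size, and whether it occurs at all, cannot be derived from the documents. A specific loss, such as 2 of 10 events, would be an assumption and not a finding. The conclusion also assumes that the EAC charter does not already override the sentence. Even if it does, the text that sites read would still need correcting.

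**What to change.** Delete the sentence. The stroke definition and the existing submission rule then govern, and they already exclude deficits with an apparent nonischemic cause. If the sponsor wants to keep a guard against counting postoperative hematomas as TEs, restate the sentence with the stroke definition's test and refer to post-surgical bleeding as Section 7.3 handles it. In either case, confirm that the EAC charter uses the same test and tell the sites.

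Do not add a rule sending every new neurologic deficit to the EAC. Because submission alone makes an event a suspected TE, deficits with an evident nonischemic cause would inflate that count.

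The cost is a one-sentence edit, a charter check and a note to sites. The downside is possibly a few more ambiguous cases for an existing committee.
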